3.7 Intervention (PLAN)

The intervention for this study, Planning For Your Advance Care Needs (PLAN), is a coaching-based communication information designed to be culturally competent. In PLAN, all coaching sessions will occur over the phone and be a maximum of 45 minutes to reduce patient burden. These sessions will focus on creating individualized messages and skill-building exercises based on patients' learning needs, goals, and values (as indicated on the intake form). The intervention will be delivered across three sessions, with the following modules, as based on prior communication competence coaching interventions:⁵³ (1) *Assessment* of current knowledge, motivation, and self-efficacy (action) as well as cultural and religious preferences/values surrounding EOL care (tablet-based intake questionnaire); (2) *clarification and correction of misconceptions* about EOL care and ACP; (3) *teaching* of relevant concepts (education about ACP and EOL care options); (4) *planning* (identifying goals of care, creating achievable goals of care, and creating strategies to communicate goals of care to providers and family members); (5) *rehearsal* of communication skills using role play exercises (practice question-asking, etc.); (6) *portrayal* of learned skills (patient applies learned skills in their oncology visit and/or with family members).

3.8 Interviewer Training and Instrument Administration

Interviewer Training. Staff working on this protocol have extensive experience interviewing

patients with advanced cancer in an end-of-life care settings from our previous NCI-funded studies. These fully trained, experienced interviewers will train new interviewers. Training will consist of learning the interview question prompts/guides, practice sessions, and instruction in administration of surveys, including IRB approved procedures for approaching potential study participants. Newly trained interviewers will be required to have a high degree of inter-rater-reliability (e.g., $\kappa=0.85$) with fully-trained, experienced interviewers on core assessments (e.g., religious beliefs about end-of-life medical care) before they will be allowed to collect data for the study.

Scheduling of Assessments. Study staff will contact enrolled patient study participants to schedule their interviews. Patients will be given the option to communicate about their assessments and the scheduling of the assessments via phone calls, emails, and/or text messages. Patient assessments will be scheduled to occur at the earliest convenient time for the participant following study enrollment. All baseline assessments will be given first. Then, patients will engage in their first intervention session within one week of completing a baseline assessment. The three intervention sessions will then be given approximately a week apart, taking approximately four weeks to complete. After completion of the intervention, patients will complete a post-intervention assessment within one week. Finally, a brief three month follow up will occur that extracts data from their EHR on healthcare utilization. For those in the control condition, they will receive a baseline assessment and then a “post-intervention” session four weeks later, which is the expected span of time between baseline and post-intervention assessments for those in the experimental condition. Three month follow up data extraction will occur for subjects in experimental and control conditions.

Conduct of Patient Assessments. Patients' assessments will be conducted either in person in clinic or at home, or over the telephone depending on the wishes of the patient. Interviews will be conducted in English or Spanish depending on the preference of the patient. We have previously validated all measures to be used in samples of English- and Spanish-speaking advanced cancer patients, and all assessments will be translated into Spanish through Datagain, a professional translation service which utilizes HIPAA compliant procedures and has been used in prior studies by the PI. We will document the language in which the interview was conducted. Each interview will be conducted alone with the patient to permit greater freedom of expression and will be approximately 45 minutes in length. If patients appear depleted or otherwise unable to be interviewed at that time, the interviewer will reschedule the interview at a time and place of their choosing within a few days. Considerable care has been taken to ensure that the interviews are as brief as possible. All Spanish translated materials will be submitted for IRB approval after receiving approval for the English documents.

Medical Chart Extraction. Study staff will review participating patients' medical charts during the course of the study to extract information about patients' health and disease status, healthcare, documentation of advance care directives, and referrals for palliative care during the study observation period.

Reducing Missing Data. To reduce missing data, following all assessments study staff will review the contents and scan for missing information. If missing information is found, the staff member will contact the subject or review the medical chart to fill-in missing data.

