3.6 Interviews, Focus Groups, Surveys, and/or Observations

A. Administration

- *Timing and Frequency*

Pre-interview/baseline assessment, intervention, and post assessment follow up post-intervention (within a week).

- *Location*

Telephone-based delivery of the intervention and in person or over the phone assessments. Cancer patients may opt to have their interview(s) during infusion at participating sites (FHCC, UT Southwestern/PHHS, Confluence Health).

***Additional measures to protect participants in the in-person interviews or usability testing from COVID-19 related exposure and infection.** In-person interviews will only be conducted in line with all the safety regulations and recommended procedures for vulnerable and at-risk patient populations. As such, no in person approaches will happen prior to the appropriate approval and authorization at each participating site. In the even in person approaches are approved, study personnel will ensure proper PPE is worn by approaching study staff, proper social distancing is observed, and that all patients consent to and are comfortable with in person interviews. Due to potential risks, telephone-based interviews will be promoted among participating patients, when available.

- *Person Identifiers*

Clinical variables will be collected from medical records and will include the following: cancer diagnosis and stage, treatment received, co-morbid conditions (i.e., Charlson Comorbidity Index, CCI), and Karnofsky performance status.

B. Study Instruments

Feasibility will be measured by intervention completion (Benchmark: $\geq 70\%$ complete the intervention sessions). Acceptability will be measured by a single-item question assessing helpfulness of the intervention (1 = not at all helpful, 5 = very helpful) as well an open-ended question about helpfulness of the intervention (“What was helpful about the intervention?”) (Benchmark: $\geq 70\%$ rate it as “helpful” or “very helpful”). Demographics will be measured via self-report assessing: age, gender, race, ethnicity, marital status, employment status, education, income, religion, insurance coverage, national origins (e.g., Mexican), cultural heritage, and acculturation.⁴² Clinical variables will be assessed using records from medical charts and will include the following: cancer diagnosis, treatment, site, and stage; co-morbid conditions, and Karnofsky⁴³ performance status.

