3.9 Intervention Administration

A total of 50 Latino advanced cancer patients will be enrolled in this study and randomly assigned to the intervention (n=25) or control (n=25) condition. Pre-intervention, patients'

communication goals will be assessed. Then, patient will participate in the intervention or a usual care control condition. After participating in the intervention or control condition, patients' engagement in ACP will be assessed to determine if the intervention improved ACP engagement and planning.

The intervention itself will be administered by a fully trained, licensed social worker via telephone. This interventionist will use a culturally competent communication intervention to "coach" patients in how to be motivated for and to actually engage in ACP, and will be bilingual in Spanish and English.

Patients randomized into the control group will receive usual care. For usual care, patients will engage in standard care with no modifications. Thus, ACP discussions will only occur as they do in usual clinical care (i.e. brought up in clinical encounters).

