5.1 Schedule of Assessments

Table 1. Schedule of trial events

	Baseline	Post-intervention (with 1 week of completing intervention)	3 mos. after completion of intervention	Off Study
Informed consent	X			
Demographics	X			
Clinical variables				X
Acceptability		X		
Usability		X		
Feasibility		X		
Quality of life	X	X		
Cultural beliefs (Fatalismo, personalismo, respeto)	X	X		
Familial beliefs (Familismo, filial duty)	X	X		
Religious/spiritual beliefs (Religious coping, religious beliefs about end-of-life medical care)	X	X		
Terminal illness acceptance	X	X		
Illness understanding	X	X		
Readiness for ACP	X	X		
Engagement in ACP	X	X		
Healthcare utilization	X	X	X	
Goal-concordant care	X	X	X	

6. Data Reporting / Regulatory Considerations

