6.2.5 Record Retention

Essential documents are those documents that individually and collectively permit evaluation of the study and quality of the data produced. After completion of the study, all documents and data relating to the study will be kept in an orderly manner by the Investigator in a secure study file. Essential documents should be retained for 2 years after the final marketing approval in an ICH region or for at least 2 years since the discontinuation of clinical development of the IP. In addition, all subject medical records and other source documentation will be kept for the maximum time permitted by the hospital, institution, or medical practice.

7. Statistical Considerations

Participants (N=50) will be randomly assigned to the intervention group (n=25) or the control group (n=25). They will then complete measures of engagement in ACP post-intervention. Feasibility and acceptability will be examined with frequency and descriptive statistics (i.e., mean, median, standard deviation, range) for enrollment rates, number of sessions completed, number of weeks required to complete the intervention, and Likert-scale items assessing satisfaction with the intervention and perceived helpfulness. Because this is a pilot study, in accordance with published standards for pilot feasibility clinical trials,⁵⁴ inferential statistics on measures of feasibility ($\geq 70\%$ intervention completion rates) and acceptability ($\geq 70\%$ rate it as "helpful" or "very helpful") are not recommended. Rather, we will examine the average rates of completion

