as well as satisfaction and helpfulness ratings to determine feasibility and acceptability based on those values being equal to or greater than 70%. We will also conduct qualitative analyses on the open-ended questions related to helpfulness. Thematic analysis using an iterative process will be conducted for all qualitative analyses.⁵⁵⁻⁵⁹ A coding scheme and codebook will be created to analyze transcripts of the responses to the open-ended question. Transcripts will be coded separately by two individual coders for manifest (e.g., frequencies) and latent (e.g., underlying themes) variables. If discrepancies occur, a third coder will resolve these conflicts. Interviews will continue until thematic saturation is achieved.^{60,61} Based on our prior field testing of interventions with patients with advanced illness, we anticipate reaching saturation with n=10 participants. Thus, n=25 in the experimental condition should be well powered to reach thematic saturation.

To examine potential efficacy, preliminary analyses will utilize t-tests to compare the two groups on baseline characteristics (e.g., education, age). Using a criterion of $p < .10$, any variables that are different among the groups will be included in the final logistic regression models as potential confounders. To test the study aim, five separate logistic regression models will be run in which ACP outcomes (yes/no to EOL discussions with family and providers; and the completion of advance directives DNR, health care proxy, and living will) will be predicted by the group variable (CCC intervention vs. control). The statistical power of the proposed logistic regressions to detect a minimum odds ratio of 2.0 for dichotomous outcome measures of ACP, for a two-tailed test with power $(1 - \beta)$ equal to 0.80, and $\alpha = 0.05$, requires a sample size of 113. Our proposed sample size of n=50 will be underpowered if the effect size is small but adequately powered if it is large. However, this study is a preliminary pilot and the main focus and goal of this is to determine feasibility, acceptability, and to provide preliminary data to inform a fully-powered RCT in future research (R01 submission).

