In addition, participants may find engagement in the intervention to be upsetting, particularly due to the potential for family conflict to arise. In addition, discussing advance care planning and end-of-life goals of care can be difficult. Patients will be in weekly contact with study interventionists who will be licensed social workers with experience working with medically ill patients and their families. These social workers will have the skills to assess exacerbations in distress in study participants and provide appropriate support. Additionally, the social workers will provide patients with continued support throughout the intervention. In the event a study participant requires a higher level of care than provided in this study, a FHCC licensed on call psychiatrist or mental health professional, UT Southwestern Licensed Clinical Psychologist, or a Confluence Health licensed on call psychiatrist or mental health professional will be consulted and the participant will be referred to the appropriate level of care. [name] (PI) will also be contacted if a patient endorses suicidal ideation. If additional intervention is necessary, [name] will coordinate with FHCC's clinical team for referral and care, [name] will coordinate with UT Southwestern's Psychiatry Department, and [name] will coordinate with a mental health professional at Confluence Health. Study participants

who express a desire following the post-intervention interview to talk at greater length about issues raised during the study will be encouraged to call study staff at the telephone number provided, and should they want a referral for psychological counseling, study staff will provide them with a referral to a mental health professional at a location that is convenient for them.

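### The helpfulness rating is scheduled only after PLAN is completed and the 70% acceptability benchmark has no stated denominator, so by default the percentage will come from completers

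*Combined protocol and SAP*

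**What the plan says.** Patients are "randomly assigned to the intervention (n=25) or control (n=25) condition" (section 3.9). Two benchmarks apply to the PLAN arm, both in section 3.6. The first is feasibility: "Feasibility will be measured by intervention completion", with at least 70% to complete the sessions. The second is acceptability: "Acceptability will be measured by a single-item question assessing helpfulness of the intervention", scored 1 to 5, with at least 70% to rate it helpful or very helpful. An open-ended question accompanies the item.

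On timing, section 3.8 says: "After completion of the intervention, patients will complete a post-intervention assessment within one week". Table 1 (section 5.1) marks acceptability once, in the column headed "Post-intervention (with 1 week of completing intervention". Control patients have a calendar-based second assessment, four weeks after baseline. PLAN patients who do not finish have no such fallback date.

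On analysis, section 7 gives descriptive statistics for "Likert-scale items assessing satisfaction with the intervention and perceived helpfulness" and uses no inferential test. The study will "determine feasibility and acceptability based on those values being equal to or greater than 70" percent. No denominator is given. Sections 3.8 and 7.2 deal with items missed during an interview, not with patients who give no rating at all.

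**The concern.** Acceptability is part of the primary objective, and section 7 names feasibility and acceptability as the main focus of the pilot and as input to a later trial. With no test on these measures, the observed percentage set against 70% is the whole decision, so it matters whose ratings enter it.

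Patients without a rating may differ from those with one. Section 9.1 foresees that "participants may find engagement in the intervention to be upsetting, particularly due to the potential for family conflict to arise", and section 9.2.3 lets patients withdraw at any time. If some stop because they dislike PLAN, the ratings most likely to be low are the ones not collected, and the completer percentage drifts upward most when PLAN is least liked. The feasibility benchmark does not correct this. It tolerates up to 30% non-completion, and it cannot separate stopping from illness from stopping from dislike.

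**Working it through.** The 70% benchmark is a chosen threshold, so there is no plan figure to reproduce. The check asks how few helpful ratings can satisfy it if only completers rate.

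Inputs:
- PLAN arm: 25 patients (section 3.9).
- Feasibility: at least 70% complete (section 3.6). 0.70 × 25 = 17.5, so at least 18 of 25 (72%).
- Acceptability: at least 70% of raters (section 3.6).
- Number of completers, c: the documents give no expected completion rate. Assumption: c lies between 18, where feasibility is just met, and 25.

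Formulas:
- Fewest helpful ratings that pass, h = 0.70 × c rounded up.
- Lowest share of the PLAN arm known to find it helpful = h / 25, which takes every non-completer as not finding it helpful.
- Highest share compatible with the same data = (h + 25 − c) / 25, which takes every non-completer as having started PLAN and found it helpful.

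| Completers c | h | h / c | Lowest share h / 25 | Highest share |
|---|---|---|---|---|
| 25 | 18 | 72.0% | 18/25 = 72% | 18/25 = 72% |
| 22 | 16 | 72.7% | 16/25 = 64% | 19/25 = 76% |
| 20 | 14 | 70.0% | 14/25 = 56% | 19/25 = 76% |
| 18 | 13 | 72.2% | 13/25 = 52% | 20/25 = 80% |

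With 18 completers and 13 helpful ratings, a report would read 72% completed and 72% found it helpful, and both benchmarks would be met. The share of the whole arm finding PLAN helpful could be anywhere from 52% to 80%, because seven patients were not asked.

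Below 18 completers the floor falls further. With 17 completers, 12 ratings pass, and 12/25 = 48%. But 17/25 = 68% fails feasibility, so 52% is the lowest share at which both benchmarks are met.

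If the denominator were all 25 assigned, with a missing rating counted as not helpful, the rule would need 18 of 25 (72%) whatever the completion rate.

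**The case against.** A reader might infer that the plan excludes early stoppers by rule, so that they can never count against acceptability. The documents do not say that. The denominator is unstated, and some text leans the other way: section 7 treats all 25 PLAN patients as a source of answers to the open-ended helpfulness question, and section 3.9 places the assessment of ACP engagement after participation, without mentioning completion. This stands. The completers-only figure is the default produced by the schedule and the lack of a rule for missing ratings.

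A reader might also take 52% as the expected result. It is a floor. It needs both benchmarks only just met and none of the seven non-completers finding PLAN helpful, although some patients with advanced cancer may stop because of illness.

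The link from upset to stopping is inferred. Section 9.1 reports minimal distress in prior studies, section 8.1 expects adverse events in under 2% of cases, and the social worker gives support throughout. Reasons for refusal and loss to follow-up are tracked (section 3.5) and adverse events are logged (section 8.2). These points lower the likely harm, but none of this information enters the 70% rule.

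Non-completers do count against feasibility, and a careful reader given 18/25 and 13/18 can work out 13/25. What that reader cannot recover is what the other seven thought.

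Finally, scoring every non-rater as not helpful, as the only rule, would be open to dispute. It penalises the same patient under both benchmarks and could bias acceptability downward. That objection is sound, so such scoring belongs in a bound shown beside the main figure.

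**Conclusion.** The point holds as a gap in scheduling and definition. The only helpfulness rating is tied to completing PLAN, none is scheduled for early stoppers, and the denominator is not stated. Followed as written, the percentage compared with 70% will by default be a completer figure, likely biased upward if patients who dislike PLAN stop. The documents do not show how many will stop or why, so the size can only be bounded: both benchmarks can be met with 52% of the arm known to find PLAN helpful at 18 completers, 56% at 20, 64% at 22 and 72% at 25. With full completion the problem disappears.

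Patients who decline before the first session have no experience of PLAN to rate. They belong under feasibility and in the all-assigned figure, and the point does not extend to counting them as acceptability failures in the main figure. This is an inexpensive improvement to a primary pilot outcome.

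**What to change.** In sections 3.6 and 3.8 and in Table 1, provide for the helpfulness item and the open-ended question to be sought by phone from every willing PLAN patient who had at least one session, including those who stop early.

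In section 7, state the denominator. Report the benchmark on all patients who started PLAN, with the number who gave no rating and the reasons (death, illness, refusal, unreachable). Beside it show:
- the completers-only figure;
- the all-assigned figure (n=25) with non-raters counted as not helpful, labelled as a conservative bound.

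Patients who decline before session 1 stay under feasibility and in the all-assigned figure.

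The cost is a few short calls by existing staff, at most 25 − 18 = 7 if feasibility is met, plus a few sentences of text. Telephone assessment is already allowed. The downside is that the reported acceptability figure may be lower.

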3.1 Overall Design

Following Phase IIb of the ORBIT model,⁴⁰ we will pilot test the developed intervention (PLAN) to demonstrate feasibility, acceptability, and preliminary effectiveness at improving patients' engagement in ACP. To assess this, 50 Latino advanced cancer patients will be recruited and randomly assigned to the intervention group (n=25) or the control group (n=25). After completing the intervention/control, patients will fill out measures of completion of end-of-life discussions and advance directives (confirmed via medical charts). Phase III (of the ORBIT model)⁴⁰ (Efficacy) will be tested in a future R01 RCT.

[figure not shown]
Because this is a protocol being transferred from Weill Cornell to FHCC, the PI ([name]) requested that two additional sites (UT Southwestern and Confluence Health) be added to the protocol to ensure the proper number of Latino patients can be enrolled in this study. Confluence Health reports a base rate population of 58% Latino patients. UT Southwestern (UTSW) has been a prior collaborator of the PI and her collaborators at Weill Cornell on R01 projects examining advanced cancer patients over time. In this prior work, they have consistently recruited several Latinx advanced cancer patients successfully and met all recruitment goals (often n=50 to 75 patients within 12 to 18 months). Additionally, [name] has collaborated on this research and has several publications in the area of end-of-life care. Finally, the current number of eligible Latinx advanced cancer patients at this site is n=15 to 20 patients per week. Finally, of great importance, UT Southwestern has trained and devoted bi-lingual research staff to assist with study recruitment. These features of the site and the lead collaborator, [name], make it a highly feasible collaborative site for this multi-site project. [name] is the founder of palliative medicine programs at UTSW and currently serves as the Medical Director of ambulatory and inpatient palliative medicine programs for the Parkland Health and Hospital System (PHHS). Additionally, this site is expected to serve as a site for future R01 submissions, thus inclusion at this point will enhance the ability to demonstrate feasibility. This request was approved by the NCI PO for this K07 award.

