will be measured using a 5-item scale assessing the degree of family loyalty and cohesion. Related to *familismo*, *filial duty*⁴⁹ will be measured with a 6-item scale assessing the degree to which children should be involved in caring for their elderly parents. Religious/spiritual beliefs will be measured with two scales: (1) *Religious coping* will be measured using *Pargament's brief RCOPE*,⁵⁰ which is a validated 14-item scale ($\alpha > .80$ ⁵⁰) assessing the extent to which patients engage in 7 types of positive and 7 types of negative religious coping. (2) *Religious beliefs about EOL medical care* will be measured using a 9-item scale. We have recently begun to validate this scale among advanced cancer patients in our prior studies.⁵¹ Potential confounders to be measured include *terminal illness acceptance*, which will be assessed using our validated, single-item question,^{19,52} which asks patients how they would define their current health status and *illness understanding*, a single item measure that assesses understanding of incurability of illness. We will use the Advance Care Planning Engagement Survey, which is a validated 49-item scale ($\alpha=.94$)¹ designed to assess knowledge, readiness/motivation, and self-efficacy of ACP. Engagement in ACP will measure two key elements of ACP. First, *EOL care discussions* will be measured by asking patients to self-report whether they have discussed any of the following: (1) wishes they have about the care they would like to receive if they were dying and/or (2) advance care directives, with an oncology provider or family member: DNR orders, living wills, durable powers of attorney for health care, assignments of health care proxies (yes/no format). Second, *completion of advance directives* will be assessed by examining the medical chart for completed advance directive documents (DNR order, living will, durable power of attorney, health care proxy). Patient's Medical Status. Patients' current and past cancer diagnoses, the dates of each, patients' Karnofsky performance score⁴³ and the number and type of oncology providers seen at that clinic will be obtained from the patient's medical chart. Advance Directives and Referrals for Palliative Care. Patient's medical charts will be reviewed for documentation of advance directives and referrals for palliative care during the study observation period (consent to interview).

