8.6 Plans for Assuring Data Accuracy and Protocol Compliance

Study data will be entered by a research assistant trained to enter data into a password-protected, secure database. A percentage (5%) of overall data entry will be entered a second time, by a different study team member to assure data accuracy. The PI will oversee first and second pass data entry and will generate reports based on data entered. The reports enable the PI to oversee data entry and level of accuracy as well as percentage of error in data entry. These reports will be generated on a regular basis and discussed with Co-Investigators.

Protocol compliance will be monitored at the weekly project staff meetings. The PI will meet with the study staff, convened via conference call, on a weekly basis to train and ensure adherence to the intended protocol. The PI will be responsible for updating all investigators regarding any study related issues that arise of that need to be addressed.

9. Unanticipated Problems Involving Risks to Subjects or Others

9.1 Potential Risks: The risks involved in this study are minimal. There are no risks of physical injury. We anticipate that there may be questions in the interview that some study participants find upsetting. However, based on interviewing patients with advanced cancers in prior NCI-funded studies, we do not anticipate that this will be problematic. Should participants become exceedingly upset, overwhelmed or fatigued, or need to attend to matters of personal care during the interview, interviewers will be instructed to ask the participant if he or she would like to take a break or reschedule the interview for another time. However, across all prior studies (PI: [name]), distress caused by engaging in these conversations has been minimal.

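### Three of the five efficacy outcomes come from chart review that is not masked, standardised or tied to an equal window in both arms, so ascertainment could differ by arm, most plausibly in favour of PLAN

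*Combined protocol and SAP*

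**What the plan says.** Section 7 specifies five logistic models. Two concern end-of-life discussions; the other three concern "the completion of advance directives DNR, health care proxy, and living will". Section 3.6 says directive completion "will be assessed by examining the medical chart for completed advance directive documents". Section 3.1 puts it slightly differently: patients report completion, with "advance directives (confirmed via medical charts" as the check.

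- **Who and when.** Section 3.8 (Medical Chart Extraction) has study staff review "medical charts during the course of the study to extract information about" health status, care, directives and palliative referrals. Section 3.6 bounds the review: documentation counts if it falls "during the study observation period (consent to interview").
- **Staffing.** Section 3.5 has FHCC study staff run both the assessments and the telephone intervention. For UT Southwestern patients, the Fred Hutch coordinator and the social worker carry out everything after consent.
- **Checks.** The inter-rater criterion in section 3.8 (kappa, for example 0.85) requires new interviewers to agree "with fully-trained, experienced interviewers on core assessments (e.g., religious beliefs about end-of-life medical care) before they will be allowed to collect data". Section 8.6 adds that "A percentage (5%) of overall data entry will be entered a second time". Section 7 has two coders for the open-ended transcripts.

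The documents describe no masking of chart reviewers, no extraction form, no list of chart locations, no definition of a completed document and no extraction date per patient.

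**The concern.** The three directive outcomes are the only modelled outcomes that do not depend wholly on patient report, so a reader will give them the most weight. Chart review still needs search and judgement: where to look, whether a document is complete, and whether it falls in the window. Two features of the plan add to the judgement. Section 3.6 lists four document types, including durable power of attorney, while section 7 models three. Section 3.4 deliberately keeps patients who already have directives.

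Two routes could make ascertainment differ by arm. First, staff who probably know the arm, and who spend three coaching sessions with PLAN patients, have more occasions to learn that a document exists and to look for it. Second, the chart may be open for longer in PLAN than in control. Either would make an odds ratio partly a measure of how, or for how long, charts were searched. Section 7 says the pilot data are to inform a fully powered trial, so a distorted odds ratio would carry forward even if no significance is claimed.

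**Working it through.** The plan gives no figure on chart ascertainment to reproduce. Its sample size of 113 concerns power and is not used here.

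**1. Do the existing checks reach the chart search?**

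| Check | Section | What it tests |
|---|---|---|
| Kappa, e.g. 0.85 | 3.8 | New interviewers on core assessments |
| 5% second entry | 8.6 | Keying of data already collected |
| Two coders | 7 | Open-ended transcripts |

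None would detect a document missed in a chart.

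**2. Is the window equal?** Section 3.8 sets the control post-assessment four weeks after baseline. For PLAN, the first session is within one week of baseline, the sessions take about four weeks, and the post-assessment follows within one week: 1 + 4 + 1 = up to about 6 weeks. The participant duration of 4 to 6 weeks in section 1 fits this. Section 3.8 also calls four weeks the expected span for PLAN, so six is an upper reading. If new documents accrued at a constant low rate (an assumption), the extreme case would give PLAN about 6/4 = 1.5 times as many.

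**3. What could unequal search do?** Let p be the true rate in both arms (no effect), and let s1 and s0 be the share of existing documents found in PLAN and control. The observed rates are p·s1 and p·s0, and

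OR = [p·s1/(1 − p·s1)] / [p·s0/(1 − p·s0)].

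The documents give no values for s1 or s0; all are assumed. The rates 4% (proxy) and 9% (living will) are the background figures for Latinos in section 2. The 30% is an assumed higher rate.

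| True rate | s1 vs s0 | Observed rates | OR |
|---|---|---|---|
| 30% | 95% vs 80% | 28.5% vs 24.0% | 0.3986/0.3158 = 1.26 |
| 30% | 100% vs 80% | 30.0% vs 24.0% | 0.4286/0.3158 = 1.36 |
| 30% | 95% vs 70% | 28.5% vs 21.0% | 0.3986/0.2658 = 1.50 |
| 9% | 95% vs 80% | 8.55% vs 7.2% | 0.0935/0.0776 = 1.21 |
| 4% | 95% vs 80% | 3.8% vs 3.2% | 0.0395/0.0331 = 1.19 |
| any | 90% vs 90% | equal | 1.00 |

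The last row shows that incomplete search alone creates no false difference. Only unequal search does.

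**4. False positives.** This is the exact binomial rejection probability of a two-sided pooled z-test at 0.05 with 25 per arm and no true effect.

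| True rate | Full search in both arms | 95% vs 75% | 100% vs 50% |
|---|---|---|---|
| 9% | 4.5% | 4.4% | 6.8% |
| 32% | 5.4% | 8.4% | 27.4% |
| 50% | 6.5% | 13.0% | 47.9% |

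At 9%, a gap of 95% vs 75% gives an OR of 1.29 but leaves the rejection rate where it was. At low rates the distortion therefore falls mainly on the odds ratio.

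**The case against.** The strongest reply is that both arms are handled alike at the point that matters. Controls receive the same post-assessment, section 3.1 has directive completion confirmed by chart in both conditions, and the missing-data check in section 3.8 follows all assessments. Staff therefore get a cue about documents from controls too. This stands, and it narrows the asymmetry to the extra contact in the PLAN sessions and the possibly longer window.

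Several stronger readings are tempting but not supported:

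- **That staff are stated to be unmasked and search charts on a rolling basis.** The protocol is silent on masking; knowledge of arm is inferred from shared staffing. Review during the study does not mean repeated searching, and section 3.6 bounds the window.
- **That the odds ratios are biased towards PLAN.** No search sensitivity appears in the documents. This is a risk with a plausible direction.
- **That swings from one document prove the point.** With 25 per arm, one missed control document turns 6/25 vs 2/25 (OR 3.6) into 6/25 vs 1/25 (OR 7.6), but one missed PLAN document turns 5/25 vs 1/25 (OR 6.0) into 4/25 vs 1/25 (OR 4.6). That is sparse data, and masked extraction would share it.
- **That the kappa criterion should be extended to a small set of charts.** In 10 charts the chance of no proxy is 0.96^10 = 66%, and of no living will 0.91^10 = 39%. Kappa would often be undefined or unstable, and a second reader would be needed.

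It is also fair that section 7 makes feasibility and acceptability the main aim, and that no go/no-go rule uses these odds ratios. That limits the weight of the point but does not remove it, since a later adjustment could not reliably repair unequal ascertainment.

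**Conclusion.** The concern holds as a risk of unequal ascertainment in three of the five efficacy outcomes, through probable knowledge of arm and a window that can run to about six weeks in PLAN against four in control. The most plausible direction favours PLAN. The size is unknown. Under assumed search sensitivities of 95% vs 80% and no true effect, the apparent odds ratio is 1.26 at a true rate of 30% and about 1.2 at 4% to 9%. At those low rates the estimate is affected more than the false-positive rate.

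The conclusion rests on three assumptions: that silence on masking together with shared staffing means reviewers usually know the arm; that PLAN contact makes a document more likely to be looked for; and that the interview ending the chart window is the post-assessment. It is a cheap improvement worth making, not a flaw that undermines the pilot's main aims.

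**What to change.** In sections 3.6 and 3.8, state that directives are extracted once per patient, over a window of the same fixed length from baseline in both arms, and only after that window has closed.

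Use existing staff who did not coach or interview that patient, where available. Candidates already in the documents are the UT Southwestern staff, who section 3.5 says are not involved after consent, and the data-entry staff in section 8.6. The documents do not show that such a person exists for every patient and site, hence the qualification. Give them a list of study IDs and window dates without arm, and one form that names the chart locations to search and says what counts as a completed document, including how a durable power of attorney is classified. Align section 3.1 (patient report confirmed by chart) with section 3.6 (chart examination) in the same edit. No kappa requirement on a small chart sample is proposed.

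The cost is protocol wording, a one-page form and a list without arm. The sample size, the intervention and the models do not change. The downsides are that extraction waits for a set date and that masking may be partial if chart notes reveal the arm; the single date, equal window and common form still make the search alike in both arms.
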